12.2.2 APOE Genotype and other DNA Markers

DNA will be extracted from participant blood samples at the screening visit and will be analyzed for APOE genotype. This will allow secondary analyses of data on the impact of the APOE genotype on putative biomarkers of AD, clinical outcome measures, and adverse events. APOE polymorphisms are an important genetic risk factor for AD. Individuals with one or two Apolipoprotein epsilon 4 (APOE4) alleles have a higher risk of developing AD and an earlier age of onset. Furthermore, those with one or two APOE4 alleles exhibit a more rapid rate of clinical change in some, but not all studies.

Blood is collected in a uniform fashion using EDTA as anti-coagulant, as described in Section 12.2.3. Once blood is collected into a 10 mL EDTA plastic tube, it is shipped overnight at ambient temperature to the ADCS Biomarker Core for APOE genotyping. Participants will be asked to consent to optional DNA banking for future research studies.

12.2.3 Plasma for Biomarkers and Pharmacokinetics

Plasma samples will be collected at screening visit and during the confinement visit every 2 hours for analysis of AD biomarkers (e.g., A β 40 & 42 and exploratory biomarkers), cholinesterase inhibition, and drug level analyses.

Biomarker and PK analyses at the screening visit will be performed on the 10 ml EDTA plastic tube whose collection is described in Section 12.2.2.

In addition, 10 ml of blood will be collected in a uniform fashion into 10mL lavender top EDTA tubes at hours 0, 2, 4, 6, 8, 10, 12, 14, 16, 18, 20, 22, 24, 26, 28, 30, 32, 34, and 36 during the confinement visit. Once blood is collected, it should be centrifuged at 1500 x g for 10 minutes at room temperature. 2 ml of plasma should be aliquoted into 2.0 ml freezer tubes, frozen at -80°, and shipped overnight on dry ice to the ADCS Biomarker Core.

At the last collection (36 hours), an extra 9mL of whole blood should be sent to the central lab for metabolic panel and CBC/Diff.

Plasma samples will be banked in the biospecimen repository of the ADCS Biomarker Core for future research studies; access to samples will be granted according to SOPs established by the ADCS Biomarker Core.

12.2.4 DNA/Genome Wide Association Studies (GWAS)/APOE Sample

A single 10 mL EDTA tube of whole blood will be collected for DNA/GWAS and APOE genotyping and epigenetic analysis at the screening visit. The EDTA tube will be shipped overnight at ambient temperature to the ADCS Biomarker Core and processed per SOP for APOE genotyping. If the sample condition is compromised or if there is poor sample yield, subjects will be asked to agree to re-sampling.

In addition, subjects will be asked to consent to optional DNA banking for future research studies. The DNA will be extracted and banked in biospecimen repository of the ADCS Biomarker Core.

13 PERSONNEL REQUIREMENTS

The site PI is responsible for the overall conduct of the study at the site. The PI is to supervise project personnel and ensure that clinical raters maintain a high level of skill and accuracy in conducting assessments. Additionally, the PI will perform or supervise clinical evaluation of all subjects and ensure protocol adherence. Additional key personnel will be required, as outlined in the procedures manual.

14 ADVERSE EVENTS (AEs)

14.1 Definition

An AE is defined as per the US Code of Federal Regulation, Title 21, Part 312.32 [<http://www.accessdata.fda.gov/scripts/cdrh/cfdocs/cfcfr/cfrsearch.cfm?fr=312.32>]. An AE is any untoward medical occurrence associated with the use of a drug in humans, whether or not considered drug related.

Collection of adverse events will begin once informed consent is signed and will continue until the follow-up phone call performed on the day after discharge. Adverse events include but are not limited to: (1) worsening or change in nature, severity, or frequency of conditions or symptoms present at the start of the study; (2) Subject deterioration due to primary illness; (3) intercurrent illness; and (4) drug interaction. An abnormal laboratory value will only be reported as an AE if the investigator considers it clinically significant, or if it leads to the subject being withdrawn from the study.

The investigator should attempt to establish a diagnosis of the event based on signs, symptoms, and/or other clinical information. In such cases, the diagnosis should be documented as the AE and not the individual signs or symptoms. Symptoms and conditions present at the beginning of the study will be characterized, so that AEs can be defined as any new symptom, or any increase in frequency or severity of an existing symptom. Adverse events should be described with medical terminology so that the event can be matched against a medical coding dictionary, such as MedDRA (Medical Dictionary for Regulatory Activities).

Investigators should report their assessment of the potential relatedness of each AE to the protocol procedure, and to the investigational product, and/or drug delivery system used in the protocol.

Following questioning and evaluation, all AEs, whether determined to be related or unrelated to the study drug by a medically qualified site PI or clinician must be documented in the subject's records, in accordance with the investigator's normal clinical practice, and on the AE electronic case report form (eCRF).

14.2 Following Up on AEs

The investigator is obliged to follow subjects with AEs until the events have subsided, the conditions are considered medically stable, or the subjects are no longer available for follow up. Subjects who discontinue due to adverse experiences will be treated and followed according to established medical practice. All pertinent information will be entered into the eCRF. Adverse events will be reported to the independent DSMB, per ADCS SOPs and study DSMB Charter.

Because of the potential of additive cholinergic adverse events caused by a combination of Posiphen and cholinesterase inhibitors in some subjects, the severity of such adverse events should be carefully evaluated taking the criteria in Appendix 5 into consideration (modified from CTCAE version 4.03.)

15 SERIOUS ADVERSE EVENTS (SAE)

15.1 Definition

A SAE is defined as per the US Code of Federal Regulation, Title 21, Part 312.32 [<http://www.accessdata.fda.gov/scripts/cdrh/cfdocs/cfcfr/cfrsearch.cfm?fr=312.32>].

An adverse event or suspected adverse reaction is considered “serious” if, in the view of either the investigator or Sponsor, it results in any of the following outcomes: Death, a life-threatening adverse event, inpatient hospitalization or prolongation of existing hospitalization, a persistent or significant incapacity or substantial disruption of the ability to conduct normal life functions, or a congenital anomaly/birth defect. Important medical events that may not result in death, be life-threatening, or require hospitalization may be considered serious when, based upon appropriate medical judgment, they may jeopardize the subject and may require medical or surgical intervention to prevent one of the outcomes listed in this definition. Examples of such medical events include allergic bronchospasm requiring intensive treatment in an emergency room or at home, blood dyscrasias or convulsions that do not result in in-patient hospitalization, or the development of drug dependency or drug abuse.

15.2 Reporting SAEs

Collection of serious adverse events will begin once informed consent is signed (regardless of study drug exposure) and will continue until 30 days following the last dose of study drug. All SAEs must be reported to the Medical Monitor, Project Directors and the Coordinating Center within 24 hours of learning of the event. This in turn will trigger an alert to the appropriate Coordinating Center personnel and Protocol Project Directors, which will lead to the initiation of the creation of the report. A notification will be sent to all participating sites and the DSMB once the report is available. Sites will inform their IRB of the event based on local IRB requirements. Annovis Bio, Inc. the IND holder is responsible for submitting any SAEs according to the FDA reporting requirements.

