Outcome measures to assess pharmacodynamics: Transcriptional inhibition of the APP gene will result in decreased production of APP, which may be reflected by decreased secretion of the processed parts fragments of APP, namely sAPP and A β , in CSF. We have selected A β 40 as a primary outcome measure because it has a relatively high concentration in CSF and is unaffected by the deposition of A β as plaques in the brain, which will be present in the study population. We also will measure secreted forms of APP (sAPP α and sAPP β) and levels of tau in CSF as secondary outcome measures. sAPP reflects processing of APP by α -secretase to

produce sAPP α and β -secretase (BACE) to produce sAPP β . Tau levels are being measured since tau transcription may be under the regulation of a similar IRE that may also be affected by Posiphen treatment.

Safety outcome measures: Reports of adverse events (AEs) and serious adverse events (SAEs) during exposure to Posiphen will be collected to evaluate if there are any significant clinical safety issues for the study population. All SAEs occurring up to 30 days after last study drug administration that are considered drug-related must also be reported. Extensive clinical and laboratory safety data already exist for Posiphen, therefore, this approach will be sufficient in the proposed study.

Clinical and cognitive assessment measures: Although clinical benefit is unlikely due to the short duration of this study, standard cognitive measures (MMSE, Logical Memory subtest of the Wechsler memory Scale (Story 1 only), and ADAS-cog) will be collected to describe the study cohort, which allows comparison to subjects in other clinical trials. It is predicted that cognition will remain stable over the course of drug exposure; however, this will be assessed formally in clinic.

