9.5.2 Confinement Visit

The confinement visit will last just over 2 days and will consist of four phases: admission, 36-hour sampling, 12-hour observation, and discharge. Subjects will be provided with meals (note: some restrictions are specified below) and sleeping accommodations during this visit. For a complete list of all visit procedures, refer to the Schedule of Events (Appendix 1) and to the Confinement Visit Diagram (Appendix 3).

Phase 1: Admission

Subjects should arrive fasted in the early morning after an overnight fast. Clinical safety labs will be drawn and sent to the local lab for analysis.

Study drug compliance over the preceding days will be assessed. If there is an insufficient level of drug compliance (less than 80% overall and or less than 80% in the last week), the site must consult with the Project Directors and Medical Monitor regarding timing and conduct of the remaining confinement visit procedures. It is possible that subjects will be discontinued early from the study due to insufficient study drug compliance.

Admission visit procedures include conducting a brief Physical and Neurological Exam, collecting vital signs, reviewing and recording adverse events and concurrent medications. Please refer to Appendix 3.1, Confinement Visit Phase 1: Admission Diagram.

Phase 2: 36-Hour Sampling

For an overview of the 36-Hour Sampling time points, please refer to the Confinement Visit Schedule of Events (Appendix 3.2b).

If no medical or compliance concerns are identified during the admission procedures, the subject will move on to the 36-Hour Sampling Phase, which entails the following procedures:

1. Place an intravenous line (for infusion) as well as a second venous line for blood sampling
2. Place the CSF catheter
3. Collect initial samples of blood and CSF

4. Administer assigned study drug (will vary based on blinded treatment assignments) at 0 hours
5. Begin the $^{13}\text{C}_6$ -labeled “heavy” leucine infusion. Subjects will receive an initial bolus of 3 mg/kg over 10 minutes, followed by 8 hours and 50 minutes of continuous intravenous infusion at a rate of 2 mg/kg/hour. The total leucine administration with the bolus is 9 hours
6. Provide a low leucine meal (NOTE: all food provided during the heavy leucine infusion must conform to low leucine dietary guidelines; refer to Appendix 4, Sample Low Leucine Menu and to the Procedures Manual for more details)
7. Continue with the following for 36 hours:

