 - a. Collect CSF (6 mL) and blood (10mL) every 2 hours at the following time points: 0, 2, 4, 6, 8, 10, 12, 14, 16, 18, 20, 22, 24, 26, 28, 30, 32, 34 and 36 hours; all collection times should be calculated from the start of the heavy leucine infusion. Samples should be in separate tubes and sent to the ADCS Biomarker Core
NOTE: If unable to obtain a total of 6 mL CSF at any given collection time (e.g., due to participant headache or participant’s CSF production level) please obtain the maximum amount possible and notify ADCS Clinical Operations
 - b. At 0 hours, an additional 1-2 ml CSF (or volume per Local laboratory requirements) should be sent ambient to the local laboratory for protein, glucose, and cell counts
 - c. Perform safety monitoring every 4 hours while the subject is awake. This includes questions about any symptoms in relation to the CSF catheter (including potential adverse events such as leg or back pain, dizziness or headaches) and vital sign monitoring. Participants also should be asked about pain, redness or swelling at the IV site in the arm
 - d. Administer assigned study drug (will vary based on blinded treatment assignments) every 8 hours – at 8, 16, 24, and 32 hours
 - e. Provide low leucine meals and snacks as needed during the duration of the heavy leucine infusion; return to normal diet after completion of the infusion (Refer to Appendix 4, Sample Low Leucine Menu)
 - f. Subjects remain at bedrest throughout the CSF sampling period of 36 hours. They are allowed to use a bedside commode for toileting
8. 36 hours after the start of the heavy leucine infusion, collect the final blood and CSF samples. An extra 9mL of whole blood should be sent to the central lab for the metabolic panel and a CBC/Diff. An extra 2mL of CSF should be sent to the local lab for protein, glucose, and cell counts
9. Remove the blood and LP catheters
10. Perform final safety monitoring, a brief physical and a brief Neurological Exam

If the subject experiences intolerable AE(s) that require early discontinuation of the sampling procedures and removal of the LP catheter, contact the Medical Monitor and Project Directors as soon as possible to discuss the situation. If feasible, the standard 12-hour observation and discharge procedures should be followed to allow for management and follow-up on the adverse events.

Phase 3: 12-Hour Observation

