The subject should be observed for at least 2 hours following removal of the LP catheter. Subjects are allowed to be up and out of bed during this period. The Research Satisfaction Survey should also be administered.

Any clinical safety labs from the pre-confinement visit that were clinically high should be repeated and sent to the local laboratory. A blood patch will be administered as required if a subject exhibits signs of a post-spinal tap headache that is not managed with bed rest, oral and intravenous fluids, caffeine, and/or mild analgesics (e.g., Ibuprofen, Naproxen or Tylenol).

Do not continue administration of study drug after completion of the 36-Hour Sampling Phase. All used and unused study drug should be returned to the clinical site for final accountability. Please refer to Appendix 3.3, Confinement Visit Phase 3:12-Hour Observation Diagram.

Phase 4: Discharge

Prior to discharge, vital signs should be recorded and a review of AE(s) and Concurrent Medications should be conducted. Upon determination by the investigator (or qualified designee) that the subject is stable, the participant will be discharged. If a participant experiences an unstable AE, please contact the Medical Monitor and Project Directors for guidance on the appropriate course of action to be taken. Please refer to Appendix 3.4, Confinement Visit Phase 4: Discharge Diagram.

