9.5.3 Post-Confinement 24-Hour Phone Follow-up

Approximately 24 hours following discharge from the Confinement Visit the subject or a person designated to speak for them will be contacted by phone to confirm the subject's well-being and to query about any new AEs.

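### SAEs are to be collected for 30 days after the last dose, but the last scheduled contact comes 30 to 40 hours after it, and Section 4 narrows which SAEs count in that period

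*Protocol*

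**What the plan says.** **SAE window and scope.** Protocol Section 15.2 starts SAE collection at consent and says that it "will continue until 30 days following the last dose of study drug". It adds: "All SAEs must be reported to the Medical Monitor, Project Directors and the Coordinating Center within 24 hours of learning of the event". Neither sentence limits reporting by relatedness.

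**A different scope in Section 4.** The paragraph on safety outcome measures covers AEs and SAEs during exposure, then says: "All SAEs occurring up to 30 days after last study drug administration that are considered drug-related must also be reported".

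**Last contact.** Section 9.5.3: "Approximately 24 hours following discharge from the Confinement Visit the subject or a person designated to speak for them will be contacted by phone". Appendix 1 (Schedule of Events) lists nothing after this call. Section 14.1 ends ordinary AE collection at the same point; it "will continue until the follow-up phone call performed on the day after discharge".

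**Timing of the last dose.** Section 9.5.2 gives study drug at hour 0 and then "every 8 hours – at 8, 16, 24, and 32 hours". After sampling the instruction is: "Do not continue administration of study drug after completion of the 36-Hour Sampling Phase". The visit has "four phases: admission, 36-hour sampling, 12-hour observation, and discharge", although the observation text itself requires only 2 hours after catheter removal.

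**Early discontinuers.** Section 10 gives them one prompt visit and no later contact.

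**SAP.** Section 5.1.1 tabulates SAEs with onset after randomization and gives no end date.

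**The concern.** Safety and tolerability are the first primary aim, and SAEs are the most important events counted under it. Two things stand in the way of a clear count.

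First, the window is 30 days long, but the plan schedules contact for less than two days of it. After the call, a new SAE enters the data only if the participant, the study partner or another care provider reports it unprompted. Participants have MCI or mild AD, with MMSE scores allowed down to 17.

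Second, the two statements of scope give different counts. Section 5.3 lists meningitis, infection, epidural or subdural bleeding and paralysis among the risks of the catheter procedure. An event of this kind could appear after discharge and be attributed to the procedure and not to the drug. That makes it the category on which Sections 4 and 15.2 differ.

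**Working it through.** The plan gives no figure for this gap, so there is none to reproduce. The check is a timeline, in hours from the start of the leucine infusion, followed by a comparison of the texts.

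**Inputs (Protocol 9.5.2, 9.5.3, 15.2)**
- Last scheduled dose: hour 32
- End of sampling: hour 36
- Observation before discharge: 12 h nominal, 2 h minimum
- Call: about 24 h after discharge
- SAE window: 30 days from the last dose

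**Formulas**
- Time of call = 36 + observation + 24
- Gap from last dose to call = time of call − 32
- Days with no scheduled contact = 30 − gap/24

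**Results**

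| Observation | Discharge | Call | Gap | Share of 30 days before the call | Days with no scheduled contact |
|---|---|---|---|---|---|
| 12 h | h 48 | h 72 | 72 − 32 = 40 h = 1.67 d | 1.67/30 = 5.6% | 30 − 1.67 = 28.33 |
| 2 h | h 38 | h 62 | 62 − 32 = 30 h = 1.25 d | 1.25/30 = 4.2% | 30 − 1.25 = 28.75 |

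**Sensitivity to the blinded capsules.** In the QD and BID groups the last active capsule may come before hour 32. The documents do not say which capsule is active, so two cases are assumed:
- Last active capsule at hour 24: the gap is 38 to 48 h, or 1.58 to 2.0 days.
- Last active capsule at hour 0: the gap is 62 to 72 h, or 2.58 to 3.0 days.

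Even in the most favourable case, 30 − 3.0 = 27 days have no scheduled contact.

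**Scope, by type of SAE after the last dose and within 30 days**

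| Judged related to | Section 15.2 | Section 4, post-dose sentence |
|---|---|---|
| Study drug | Reportable | Reportable |
| Catheter procedure only | Reportable | Not covered |
| Neither | Reportable | Not covered |

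**Does any other text supply a later contact?**
- Section 14.2 follows AEs that are already known; it does not look for new ones.
- The 24-hour reporting clock in Section 15.2 starts when the site learns of an event.
- Section 12.1.3 mentions a post-confinement visit with local laboratory samples, but Section 9.5 and Appendix 1 define only the phone call.
- For early discontinuers the gap depends on when their single visit takes place; no contact at the end of the window is planned for them either.

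**The case against.** The case on the other side has real weight.

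**On scope.** Section 4 is background. It says that drug-related SAEs must be reported in addition to those during exposure; it does not say that others must be left out. Section 15.2 is the section that governs reporting, and it covers all SAEs. Section 14.1 also asks investigators to judge relatedness to the procedure as well as to the drug. A reader might infer that catheter-related SAEs fall outside the trial's reporting. The documents do not support that: a site following Section 15.2 would report them. What stands is that Section 4 states a narrower rule for the same period, and nothing says which text prevails.

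**On detection.** A reader might infer that late SAEs will be lost. The documents do not support that either:
- A study partner with frequent contact is required (Section 8.1, criterion 11).
- The call may go to someone who speaks for the participant.
- Most SAE criteria are overt, such as death or hospitalization.
- Spontaneous reporting stays open for the full 30 days.
- The consent pages, procedures manual, coordinating center SOPs and DSMB charter were not available, and they may carry reporting instructions.

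What stands is that no scheduled contact backs the window, and no text reviewed gives the study partner a reporting task after discharge.

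**On design.** Choosing active over spontaneous follow-up is partly a preference. That limits how strongly the point can be pressed, but the added contact costs little.

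**Conclusion.** The point holds as a gap in ascertainment and an inconsistency in wording. For a participant who completes dosing at hour 32, 28.3 to 28.8 of the 30 days (94.4% to 95.8%) rely on spontaneous reporting, and the two protocol sections define the reportable SAEs in that period differently. Late SAEs can be missed.

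This rests on three assumptions: the hour-32 dose is given, the call is made on time, and no document outside those reviewed schedules a later contact.

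Two stronger conclusions are not warranted. A reader might infer that a finding of no late SAEs would carry no information; with a study partner in place and reporting open, it would carry some. A reader might also want to attach an upper confidence bound to zero events in 24 participants. Neither document plans one. The 24 combine 15 on Posiphen and 9 on placebo, so the bound would not describe risk on drug, and it would say nothing about how many events go unreported.

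This is a low-cost improvement to a primary aim and does not call the design into question.

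**What to change.** 1. **Protocol Section 4:** align the SAE sentence with Section 15.2, so that all SAEs to 30 days after the last dose count regardless of causality.
2. **Appendix 1 and Section 9.5:** add one phone contact with the participant or study partner at the end of the 30-day window. It should ask about any SAE. Limiting it to drug- or procedure-related events would create a third scope and would move the causality judgment ahead of detection.
3. **Section 10:** apply the same call to early discontinuers and replaced participants who took study drug.
4. **SAP 5.1.1:** state that the SAE tabulation ends 30 days after the last dose.

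The cost is one protocol amendment, a line in the SAP and one call per dosed participant: 24, or slightly more with replacements. No dose, procedure or endpoint changes. If the sponsor prefers not to add the call, the protocol should at least say that SAE collection after the 24-hour call is by spontaneous report.
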